12.2 Safety Meetings

The DF/HCC Data and Safety Monitoring Committee (DSMC) will review and monitor toxicity and accrual data from this trial. The committee is composed of clinical specialists with experience in oncology and who have no direct relationship with the study. Information that raises any questions about participant safety will be addressed with the Principal Investigator and study team.

The DSMC will meet quarterly and/or more often if required to review toxicity and accrual data. Information to be provided to the committee may include: up-to-date participant accrual; all grade 2 or higher unexpected adverse events that have been reported; summary of all deaths while being treated and during active follow-up; any response information; audit results, and a summary provided by the study team. Other information (e.g. scans, laboratory values) will be provided upon request.

CONFIDENTIAL

This document is confidential. Do not disclose or use except as authorized.

12.3 Monitoring

Involvement in this study as a participating investigator implies acceptance of potential audits or inspections, including source data verification, by representatives designated by the Principal Investigator (or Protocol Chair) or DF/HCC. The purpose of these audits or inspections is to examine study-related activities and documents to determine whether these activities were conducted and data were recorded, analyzed, and accurately reported in accordance with the protocol, institutional policy, Good Clinical Practice (GCP), and any applicable regulatory requirements.

All data will be monitored for timeliness of submission, completeness, and adherence to protocol requirements. Monitoring will begin at the time of participant registration and will continue during protocol performance and completion.

12.3.1 Quality Assurance and Rapid Review of Treatment Plans

To ensure protocol compliance, the treatment plans for the first three patients treated at each site will be reviewed by the Principal Investigator and Participating Site's PI. As described above, plans will be submitted to the ATC for this protocol. The plans will be sent to the ATC upon approval by the treating physician, and the PI and/or Participating Site PI will review and confirm protocol compliance within three working days of the start of treatment.

13. REGULATORY CONSIDERATIONS

13.1 Declaration of Helsinki

The PI will ensure that this study will be conducted in full conformity with the current version of the declaration of Helsinki and with U.S. FDA requirements

13.2 Patient Confidentiality

The investigators will ensure that patient anonymity is maintained.

13.3 Protocol Review and Amendments

This protocol, the proposed informed consent and all forms of participant information related to the study (e.g., advertisements used to recruit participants) and any other necessary documents must be submitted, reviewed and approved by a properly constituted IRB governing each study location.

Any changes made to the protocol must be submitted as amendments and must be approved by the lead site (DF/HCC) IRB prior to implementation. Any changes in study conduct must be reported to the IRB. The Principal Investigator (or Protocol Chair) will disseminate protocol amendment information to all participating investigators.

CONFIDENTIAL

This document is confidential. Do not disclose or use except as authorized.

All decisions of the IRB concerning the conduct of the study must be made in writing.

13.4 Informed Consent

All participants must be provided a consent form describing this study and providing sufficient information for participants to make an informed decision about their participation in this study, including an adequate explanation of the aims methods, anticipated benefits and potential hazards of the study to the patient. The formal consent of a participant, using the IRB approved consent form, must be obtained by the Principal investigator or physician co-investigator before the participant is involved in any study-related procedure. The consent form must be signed and dated by the participant or the participant's legally authorized representative, and by the person obtaining the consent. If the patient does not speak English, an interpreter will be made available and the treating institution's policy for obtaining research consent from non-English speaking patients will be followed. The informed consent process will be documented in the patient's medical record. The participant must be given a copy of the signed and dated consent document. The original signed copy of the consent document must be retained in the medical record or research file.

13.5 Ethics and Good Clinical Practice (GCP)

This study is to be conducted according to the following considerations, which represent good and sound research practice:

- ICH Consolidated Good Clinical Practice: Guidelines (E6)
www.fda.gov/cder/guidance/iche6.htm
- US Code of Federal Regulations (CFR) governing clinical study conduct and ethical principles that have their origin in the Declaration of Helsinki
 - Title 21 Part 11 – Electronic Records; Electronic Signatures
www.access.gpo.gov/nara/cfr/waisidx_02/21cfr11_02.html
 - Title 21 Part 50 – Protection of Human Subjects
www.access.gpo.gov/nara/cfr/waisidx_02/21cfr50_02.html
 - Title 21 Part 54 – Financial Disclosure by Clinical Investigators
www.access.gpo.gov/nara/cfr/waisidx_02/21cfr54_02.html
 - Title 21 Part 56 – Institutional Review Boards
www.access.gpo.gov/nara/cfr/waisidx_02/21cfr56_02.html

CONFIDENTIAL

This document is confidential. Do not disclose or use except as authorized.

- Title 21 Part 312 – Investigational New Drug Application
www.access.gpo.gov/nara/cfr/waisidx_02/21cfr312_02.html
- State laws
- Institutional research policies and procedures www.dfhcc.harvard.edu/clinical-research-support/clinical-research-operations-cro/policies-and-procedures

It is understood that deviations from the protocol should be avoided, except when necessary to eliminate an immediate hazard to a research participant. In such case, the deviation must be reported to the Principal Investigator and the IRB according to the local reporting policy.

13.6 Study Documentation

The investigator must prepare and maintain adequate and accurate case histories designed to record all observations and other data pertinent to the study for each research participant. This information enables the study to be fully documented and the study data to be subsequently verified.

Original source documents supporting entries in the case report forms include but are not limited to hospital records, clinical charts, laboratory and pharmacy records, recorded data from automated instruments, microfiches, photographic negatives, microfilm or magnetic media, and/or x-rays.

13.7 Records Retention

All study-related documents must be retained for the maximum period required by applicable federal regulations and guidelines or institutional policies.

13.8 Multi-center Guidelines

This protocol will adhere to the policies and requirements of the Dana-Farber/Harvard Cancer Center. The specific responsibilities of the Principal Investigator (or Protocol Chair), Coordinating Center, and Participating Institutions are presented in the Dana-Farber/Harvard Cancer Center Multi-Center Data and Safety Monitoring Plan (see Appendix II).

- The Principal Investigator/Coordinating Center is responsible for distributing all Safety Reports to all participating institutions for submission to their individual IRBs for action as required.
- Mechanisms will be in place to ensure quality assurance, protocol compliance, and adverse event reporting at each site.

CONFIDENTIAL

This document is confidential. Do not disclose or use except as authorized.

14. STATISTICAL CONSIDERATIONS

The primary objective is to demonstrate proton beam radiation of unresectable primary hepatocellular cancer is associated with local control of at least 80% at 2 years. The null hypothesis is based on a 2-year local control rate of 55% following treatment of tumors >3cm with radiofrequency ablation (RFA), as discussed in 2.3. However, the local control tends to be much poorer in certain subgroups, including tumors unable to be treated by RFA and the largest tumors, thus 55% is used as an upper bound for the sample size considerations.

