1.2 Primary Objectives

To demonstrate 2 yr LC of >80% with proton beam irradiation for unresectable hepatocellular cancer. This will be benchmarked against 2 yr LC of ~55% for tumors > 3cm in size with radiofrequency ablation.

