Given these promising results in otherwise incurable malignancies, the MGH group undertook a Phase I study to evaluate the use of high dose conformal proton beam irradiation for selected patients with hepatocellular cancer, cholangiocarcinoma and hepatic metastases. The dose escalation was based on a model based on the amount of radiation that the normal liver received, or equivalent uniform dose (EUD) to the liver. The eligibility criteria were 1-3 lesions, greatest less than 6 cm in size, Childs A/B, and no extrahepatic disease. Patients were treated with gated proton beam therapy using 4D treatment planning techniques. Generally, patients have been treated to a dose of 45-75 Gy (RBE) in 15 fractions. The study was a dose escalation trial based on liver EUD. The dose that each patient was treated to was based not only on the liver EUD at each step but had to comply with protocol defined normal tissue constraints (bowel, chest wall). To date, there have been no local failures or radiation-induced liver disease through 3 of the first 4 dose levels.

CONFIDENTIAL

This document is confidential. Do not disclose or use except as authorized.

Because of the limitations of the EUD based liver concept as a dose escalation platform, as well as the non dose-limiting nature of liver with proton therapy, we have decided to proceed with a modification of the approach taken by the Tsukuba group (13). Investigators at Tsukuba have treated 165 patients (192 tumors) with a similar 15 fraction protocol to a median dose of 72 Gy. Patients with tumor sizes of 10 cm or greater were allowed on the study. Central tumors (within 2 cm of the porta hepatis) were treated to 66 Gy in 22 fractions because of concerns of toxicity. Local control at 5 years was an impressive 86.9%. Local control at 2 years was 90%. However 5 yr OS was only 23%, highlighting the out of field progression and comorbidities in these patients. In this study, we propose a treatment schedule of 15 fractions of proton beam radiation with an expected 2 yr LC of > 85%. Because we anticipate treating large tumors generally greater than 3 cm, we will seek to improve upon a RFA local control rate of ~ 50% to 80% with proton beam therapy.

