14.1 Study Design/Endpoints

The primary endpoint is local control at 2 years, or equivalently, the absence of local failure as defined in 10.3. Starting with a total of 60 patients with unresectable primary hepatocellular cancer, we project 30 of them will be alive at 2 years for the evaluation of local control assuming a 2-year overall survival of 50%. The number of evaluable patients is a conservative assumption based on the historical RFA data and the Tsukuba proton data (13) showing a 2-year overall survival in the range of 50-70%. Analysis of 30 patients alive at 2 years will achieve 94% power to detect a local control rate of 80% if at least 21 of them were free of local failure. The decision rule is associated with 7% probability for accepting the proton protocol is associated with improved local control when the true rate is only 55% at 2 years.

The rate of local control will be based on actuarial estimates, primarily at 2 years, using the Kaplan-Meier method. Time to local failure will be measured from the start of radiation therapy to the date of local failure, as defined in 10.3. Patients who have not failed locally will be censored at the time of last follow-up. A minimum follow-up of 2 years will be required, while patients who die or drop out of the protocol prior to 2 years will be censored at that date.

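### The primary objective is worded as demonstrating 2-year local control of 80%, but the design tests 55%, so a positive result supports only local control better than 55%

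*Combined protocol and SAP*

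**What the plan says.** Two places state the primary objective. Section 1.2: "To demonstrate 2 yr LC of >80% with proton beam irradiation for unresectable hepatocellular cancer". The opening of section 14: the treatment "is associated with local control of at least 80% at 2 years". One says more than 80%, the other at least 80%.

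The neighbouring text describes a different comparison:

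- Section 1.2, next sentence: "This will be benchmarked against 2 yr LC of ~55% for tumors > 3cm in size with radiofrequency ablation".
- Section 2.3: "we will seek to improve upon a RFA local control rate of ~ 50% to 80% with proton beam therapy".
- Section 14, next sentence: "The null hypothesis is based on a 2-year local control rate of 55" per cent, taken from radiofrequency ablation (RFA) of tumours above 3 cm.
- Section 14.1, on the projected 30 survivors: the design "will achieve 94% power to detect a local control rate of 80% if at least 21 of them were free of local failure". For this rule it gives a 7% probability of "accepting the proton protocol is associated with improved local control when the true rate is only 55% at 2 years".

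Section 14.1 then adds: "The rate of local control will be based on actuarial estimates, primarily at 2 years, using the Kaplan-Meier method". It gives no confidence interval or level for that estimate. Section 14.4 names exact binomial intervals, but only for toxicity and response rates.

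**The concern.** The primary objective is the sentence against which a result is judged. As worded, it requires the trial to demonstrate 80%, and nothing in sections 14 to 14.2 tests 80%. The rule can be met by an observed rate below the stated objective: 21, 22 or 23 of 30 is 70.0%, 73.3% or 76.7%. At 22 of 30, one reader could report success by the rule and another could report that the objective was missed, each citing the protocol. No interval is planned for the primary estimate that would show readers which rates the data support. At stake is what a positive result may conclude.

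**Working it through.** **Inputs.** Null rate 0.55 (section 14). Alternative 0.80, 30 patients alive at 2 years, acceptance at 21 or more, error 7%, power 94%, 2-year survival of 50-70% (section 14.1). 60 patients with hepatocellular cancer (sections 14.1 and 14.2).

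**Step 1: reproduce the plan's figures.** With X ~ Binomial(30, p), P(X ≥ 21) is the sum over k = 21 to 30 of C(30,k) p^k (1−p)^(30−k).

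- p = 0.55: 0.0694 (stated 7%).
- p = 0.80: 0.9389 (stated 94%).

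Both agree. The 7% is an error rate against 55%; against 80%, the same rule has no stated error rate.

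**Step 2: how often the rule is met when the true rate is below 80%.** Same formula:

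| True 2-year local control | P(rule met) |
|---|---|
| 65% | 0.36 |
| 70% | 0.59 |
| 75% | 0.80 |
| 79% | 0.92 |

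Meeting the rule therefore does not separate 80% from rates clearly below it. Conversely, if the true rate is exactly 80%, a passing count with an observed rate under 80% (21 to 23) has probability 0.9389 − 0.6070 = 0.33, where 0.6070 is P(X ≥ 24).

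**Step 3: what a passing count supports.** Exact (Clopper-Pearson) two-sided 95% limits for r of 30: the lower is the 0.025 quantile of Beta(r, 31−r), the upper the 0.975 quantile of Beta(r+1, 30−r).

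| Count | Observed | 95% CI |
|---|---|---|
| 21/30 | 70.0% | 50.6% to 85.3% |
| 22/30 | 73.3% | 54.1% to 87.7% |
| 23/30 | 76.7% | 57.7% to 90.1% |
| 24/30 | 80.0% | 61.4% to 92.3% |

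Even an observed 80% leaves rates down to about 61% open.

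**Step 4: what demonstrating 80% would take.** The exact one-sided 95% lower limit is the 0.05 quantile of Beta(r, 31−r): 76.1% at 27/30 and 80.5% at 28/30. So 28 of 30 (93%) is the first count that excludes 80%. P(X ≥ 28) is 0.15 at a true 85% and 0.41 at a true 90%. Section 2.3 expects a 2-year rate above 85%; at 85% itself, the design would seldom demonstrate 80%.

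**Step 5: limits of the reproduced error rate.** Step 1 assumes exactly 30 alive. Survival of 50-70% in 60 patients gives 30 to 42 alive. With the count of 21 kept fixed, P(X ≥ 21) at p = 0.55 is 0.15 with 32 alive, 0.41 with 36 and 0.79 with 42.

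**The case against.** The strongest reply is that the documents already settle the intent. The benchmark follows the objective directly in section 1.2, the null follows it directly in section 14, and section 14.1 describes a positive result as improved local control. Section 14.2 speaks of detecting an increase to 80%, which is the language of a design alternative. A passing count below the alternative is normal in any single-arm design whose cut-off lies between null and alternative. Sample size, cut-off, error and power are not affected.

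Most of this stands, and it limits the harm: a careful reader can infer the intended comparison. It does not correct the two sentences that state the objective, which still claim a property the design lacks.

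Three stronger readings are tempting, and the documents do not support them:

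- A reader might infer that the trial plans to claim 80% on 21 of 30. No passage ties the rule to an 80% claim.
- A reader might infer that the rule was miscalculated. The stated 7% and 94% reproduce for 30 patients.
- In the other direction, a reader might infer from that agreement that the primary test is sound and only the wording needs work. Step 5 shows that the fixed count loses error control within the plan's own survival range. Section 14.1 also does not reconcile the count among survivors with the Kaplan-Meier estimate, in which deaths are censored. Which of the two should govern is a separate question.

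**Conclusion.** The point holds as a misstated primary objective. Sections 1.2 and 14 promise a demonstration of 80%; the design can show only that local control exceeds 55%. The gap is material: the rule is met with probability 0.59 at a true 70% and 0.80 at a true 75%, while excluding 80% with 30 evaluable patients needs 28 of 30 instead of 21.

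These figures assume a binomial count in exactly 30 evaluable patients, which is the basis section 14.1 uses. The wording fault does not depend on that assumption: whichever analysis governs, the stated null is 55%. It should be fixed, because the objective determines what a positive result may conclude and the correction is cheap.

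**What to change.** Reword section 1.2 and the first sentence of section 14 to:

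> To test whether 2-year local control in unresectable hepatocellular cancer exceeds 55%, with power calculated at a true rate of 80%.

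Add to section 14.1:

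> A positive result supports 2-year local control above 55% and does not establish 80%. The 2-year Kaplan-Meier estimate is reported with a two-sided 95% confidence interval (log-log method).

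The interval lets readers see which rates the data support. It describes the result and is not a second decision rule.

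The cost is wording plus one interval from data already collected, with no extra patients. There are two downsides. The stated claim becomes less favourable. And at 21 or 22 of 30 the 95% interval can include 55% although the rule is met (exact lower limits 50.6% and 54.1%), because the rule works at a one-sided 7%; the report should say so if it happens. This rewording does not settle how the count should adapt to the number alive, or how it relates to the Kaplan-Meier analysis; those need their own resolution.

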14.1 Study Design/Endpoints

The primary endpoint is local control at 2 years, or equivalently, the absence of local failure as defined in 10.3. Starting with a total of 60 patients with unresectable primary hepatocellular cancer, we project 30 of them will be alive at 2 years for the evaluation of local control assuming a 2-year overall survival of 50%. The number of evaluable patients is a conservative assumption based on the historical RFA data and the Tsukuba proton data (13) showing a 2-year overall survival in the range of 50-70%. Analysis of 30 patients alive at 2 years will achieve 94% power to detect a local control rate of 80% if at least 21 of them were free of local failure. The decision rule is associated with 7% probability for accepting the proton protocol is associated with improved local control when the true rate is only 55% at 2 years.

The rate of local control will be based on actuarial estimates, primarily at 2 years, using the Kaplan-Meier method. Time to local failure will be measured from the start of radiation therapy to the date of local failure, as defined in 10.3. Patients who have not failed locally will be censored at the time of last follow-up. A minimum follow-up of 2 years will be required, while patients who die or drop out of the protocol prior to 2 years will be censored at that date.

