5.6 Duration of Follow Up

Study participants will be followed for five years from the completion of study treatment or until death, whichever occurs first. Participants will be removed from follow-up when any of the criteria listed in Section 5.5 apply. Participants removed from treatment or follow-up will be followed for survival outcomes and a 2 years analysis of local control.

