9. STUDY CALENDAR

9.1 Required Data

Lab evaluations must be completed within 2 weeks of study entry. All other baseline assessments must be completed within 6 weeks of study entry. All study assessments should be administered +/- 3 days of the protocol-specified date, unless otherwise noted.

Data Set	Prior to Study Entry	Weekly Visit During Radiation Therapy	At Follow-Up (3)
Age	X		
Sex	X		
H&P (including clinical assessment of ascites and encephalopathy at baseline and follow up)	X	X	X
Toxicity Assessment	X	X	X
Vital Signs (pulse, blood pressure, temperature)		X	
CBC with diff (WBC, HGB, PLT, ANC, ALC)	X	X	
PT/INR, Albumin, Child-Pugh classification	X		X
Renal Function Tests (BUN, creatinine, calculated creatinine clearance per Cockcroft & Gault)	X	X	
Liver Function Tests (SGOT, SGPT, T bili, Alk Phos) & LDH	X	X	X
Tumor markers (CEA, CA 19-9) Alpha Fetal Protein	X	X	X
Beta-HCG (women of child-bearing potential)	X		
Tumor Measurement	X		twice yearly (1)
Abdominal and Pelvic CT and/or hepatic MRI	X		twice yearly (1)
Thoracic CT	X		twice yearly
Peripheral Blood for correlative studies (optional)	X	X (2)	X (2)

Notes:

(1) Imaging and tumor measurements in follow up are required for study data twice yearly. Additional imaging studies may be obtained for clinical follow up at the discretion of the treating clinicians. For study participants who receive follow up care at institutions other than the treating institution, imaging reports and scans must be sent to the treating institution to be included in the study data set.

(2) Peripheral blood will be obtained with clinical labs at pretreatment, during proton beam radiation therapy at days 1, 8, 15 and the last day of radiation treatment. (this blood draw is optional and will be offered to study participants at MGH only)

CONFIDENTIAL

This document is confidential. Do not disclose or use except as authorized.

(3) Follow up assessments will be due at 1, 3, 6, 9, 12, 15, 18, 21, 24, 30, 36, 42, 48, 54, and 60 months post treatment, with a visit window of +/- 3 weeks for the 1 month follow up and +/- 6 weeks for all other follow up dates.

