10.3 Local Failure

CONFIDENTIAL

This document is confidential. Do not disclose or use except as authorized.

Local failure is defined as: evidence of tumor growth/regrowth in any direction beyond that present of the pre-treatment imaging studies in the treated lesion(s). Intrahepatic recurrence elsewhere in the liver is defined as any new lesion in the liver. The imaging studies are to be comparable in technical factors.

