10.7 Overall Survival

Duration measured from registration until death or censored at date of last follow-up for patients still alive.

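### Section 14.1 censors local control at last follow-up, not at the last liver scan, so patients followed without imaging can bias the estimate upward, mainly at 5 years

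*Combined protocol and SAP*

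**What the plan says.** - **Estimator (14.1).** "The rate of local control will be based on actuarial estimates, primarily at 2 years, using the Kaplan-Meier method".
- **Censoring (14.1).** "Patients who have not failed locally will be censored at the time of last follow-up". The next sentence asks for at least 2 years of follow-up and adds that "patients who die or drop out of the protocol prior to 2 years will be censored at that date".
- **Meaning of the term.** Section 10.7 uses the same expression to censor overall survival: "Duration measured from registration until death or censored at date of last follow-up for patients still alive". Read together, it means last contact alive. No section ties it to a scan.
- **Endpoint (10.3).** Local failure is growth or regrowth of a treated lesion relative to the imaging done before treatment, and "The imaging studies are to be comparable in technical factors".
- **Schedules (9.1, 9.2).** Visits fall every 3 months to month 24 and every 6 months to month 60. Section 9.1 note (1) says: "Imaging and tumor measurements in follow up are required for study data twice yearly". Section 9.2 has liver imaging twice a year for 2 years and once a year for the next 3.
- **Removal (5.5, 5.6, 5.7).** Meeting any criterion in 5.5, one of which is disease progression, ends scheduled follow-up. Then: "Participants removed from treatment or follow-up will be followed for survival outcomes and a 2 years analysis of local control". Removal from the study itself (5.7) needs death or withdrawal of consent.
- **Objectives (1.2, 1.3).** Two-year local control is primary; 5-year local control is secondary.

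**The concern.** The endpoint is observed on scans, but time at risk runs to last contact. When a patient is followed past the last liver scan, any failure in that gap cannot be recorded, yet the patient stays in the Kaplan-Meier risk set as not failed. A missed scan can hide a failure but cannot create one, so this error has one direction.

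The plan itself creates a group for whom this could happen: patients removed from scheduled follow-up for progression, including progression away from the treated lesion, who are still followed. Up to 2 years a local control analysis is intended for them, without a stated scan schedule. Beyond 2 years only survival follow-up is described. At stake are the primary comparison with the 55% benchmark and, more so, the 5-year local control estimate.

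**Working it through.** **The plan's own figures.** With X binomial, n = 30: P(X ≥ 21 | p = 0.55) = 0.0694 and P(X ≥ 21 | p = 0.80) = 0.9389. These match the stated 7% and 94%, and 60 × 0.50 = 30. The arithmetic of the rule is not in question.

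**Inputs from the documents.** Two-year local control 55% (null) and 2-year survival 50%, both from 14.1. Scans at months 6, 12, 18, 24, 36, 48 and 60, following 9.2.

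**Assumptions, not in the documents.** Constant and independent hazards for local failure, death and progression; 50% progressed by month 24; a share g of progressors stops liver scans at progression but stays in follow-up.

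**Formulas.**
- True local control: S(t) = 0.55^(t/24), so S(60) = 0.55^2.5 = 0.224.
- Progressed by t: P(t) = 1 − 0.5^(t/24). Still scanned at t: 1 − g·P(t).
- A failure arising between two scans is recorded only if the second is done: d_k = [S(t_{k−1}) − S(t_k)]·[1 − g·P(t_k)].
- Deaths shrink the risk set and the failures in proportion, so they cancel.
- Under last-follow-up censoring, patients with no recorded failure stay at risk and the product telescopes: KM(t) = 1 − Σ d_k = S(t) + g·Σ [S(t_{k−1}) − S(t_k)]·P(t_k).

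| Month | S | Drop in S | P | Drop × P |
|---|---|---|---|---|
| 6 | 0.8612 | 0.1388 | 0.1591 | 0.0221 |
| 12 | 0.7416 | 0.1196 | 0.2929 | 0.0350 |
| 18 | 0.6387 | 0.1030 | 0.4054 | 0.0417 |
| 24 | 0.5500 | 0.0887 | 0.5000 | 0.0443 |
| 36 | 0.4079 | 0.1421 | 0.6464 | 0.0919 |
| 48 | 0.3025 | 0.1054 | 0.7500 | 0.0790 |
| 60 | 0.2243 | 0.0782 | 0.8232 | 0.0643 |

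The last column sums to 0.1432 at month 24 and 0.3784 at month 60.

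| g | Survivors unscanned at month 24 (g × 0.5) | KM at 2 years: 0.55 + 0.1432g | KM at 5 years: 0.2243 + 0.3784g |
|---|---|---|---|
| 0 | 0% | 55.0% | 22.4% |
| 0.10 | 5% | 56.4% | 26.2% |
| 0.25 | 12.5% | 58.6% | 31.9% |
| 0.50 | 25% | 62.2% | 41.4% |

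Simulation of the same setting gave about 56, 59 and 62% at 2 years and 27, 32 and 42% at 5 years, within a point of these.

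**Last-scan censoring.** Only patients scanned at t_k are then at risk there, so 1 − g·P(t_k) multiplies both failures and risk set. Each factor is S(t_k)/S(t_{k−1}) and the product is S(t): 55% and 22%, whatever g is.

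**A second pattern.** Let 10, 20 or 30% of all patients have stopped scans by month 24 at a constant rate that continues afterwards. By simulation:
- True 55%: the 2-year estimate is 57.6, 60.2 or 63.3%, and the 5-year estimate (true 22%) is 31, 39 or 47%.
- True 80%: the 2-year estimate is 81.4, 82.4 or 83.8%, and the 5-year estimate (true 57%) is 63, 68 or 72%.
- Chance that the 2-year estimate from 60 patients reaches 70% (21/30) when the truth is 55%: 3% with no loss of scans, rising to 6, 11 or 19%. With last-scan censoring it is 4, 4 or 5%.

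**The case against.** The plan does a good deal to limit the problem. Twice-yearly imaging is required for study data, outside scans have to be sent in, and 5.6 intends a 2-year local control analysis even for removed patients. If all of that happens, the two censoring rules give the same 2-year answer: visits or deaths between scheduled scans add no bias, as the g = 0 row shows. The clause censoring patients who leave the protocol before 2 years might also be read to cover those removed under 5.6, which would end their time at risk at removal.

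Most of this stands for the 2-year estimate, and it is why the bias there can only be called possible. It does not close the gap. Section 14.1 has no rule for a patient whose scans stop while contact continues. The dropout clause sits uneasily with 5.6, which keeps removed patients in the 2-year analysis, and it says nothing about time after 2 years.

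The illustration also treats progression and death as independent. Section 2.3 links poor survival to progression outside the field. If progressors die sooner, they add less unscanned time and the figures above are too high.

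**Conclusion.** The point holds in conditional form. The censoring date in 14.1 does not match an endpoint read from scans, and any resulting bias is upward. It is zero with complete imaging, limited at 2 years and potentially large at 5 years. With 10 to 50% of progressors unscanned but followed, it is about 1 to 7 points at 2 years (true 55%) and 4 to 19 points at 5 years (true 22%). These sizes rest on the assumptions listed in the check, since the documents give no missed-scan rate.

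Two stronger readings are tempting and not supported:
- **That the trial's local control rates are inflated.** That depends on scans being missed, which the documents neither state nor imply for the 2-year analysis.
- **That a surviving patient without a scan is scored as controlled in the 21-of-30 rule.** Section 14.1 speaks of patients alive at 2 years for evaluation of local control and does not say how an unscanned one is scored.

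**What to change.** In 14.1:
- Censor patients without local failure at the date of their last evaluable liver imaging, on or before last contact or death.
- Base the primary 2-year conclusion on that Kaplan-Meier estimate.
- Report last-follow-up censoring as a sensitivity analysis. Last-scan censoring recovers the truth above because loss of scans was unrelated to local failure; after progression it may be informative.

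The documents should also state what imaging applies to patients removed under 5.6, and the imaging schedules after year 2 in 9.1 and 9.2 must be reconciled.

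A rule that counts a patient as free of failure only with a scan at 24 months or later should not be added. Earlier failures would count without such a scan, and patients lacking one would have no status. Re-treatment of the treated lesion is a separate question and does not belong in this change.

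**Cost.** A change of wording, using scans that 9.1 and 9.2 already place in the study data set. Some patients contribute slightly less follow-up, so the interval is slightly wider. The sample size is unchanged, and with complete imaging so is the result.
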